8. RESEARCH QUESTION AND OBJECTIVES

Research Questions:

To understand the clinical outcomes of patients treated with sunitinib in first line and axitinib in second line in a real world setting as therapies for mRCC and/or aRCC.

Primary Objective:

1. What is the PFS of patients treated in first line with sunitinib, and stratified by MSKCC/IMDC risk category (favourable, intermediate, poor)?
2. What is the PFS of patients treated in second line with axitinib, and stratified by MSKCC/IMDC risk category (favourable, intermediate, poor)?

Secondary Objectives:

First Line:

1. What is the OS of all patients in first line with sunitinib, and stratified by MSKCC risk (favourable, intermediate, poor)?
2. What is the duration of therapy with sunitinib in first line (using time TTD) for all patients and stratified by MSKCC risk (favourable, intermediate, poor).
3. ORR.
4. Duration of ORR (CR or PR).
5. Examine factors that predict duration of therapy on sunitinib (TTD), eg, risk stratification, or individual/grouped parameters that comprise the prognostic classification systems.
 - a. Less than one year from time of diagnosis.
 - b. Karnovsky performance status less than 80%.
 - c. Haemoglobin less than the lower limit of normal (eg, less than 12 g/dl).
 - d. Serum calcium great than the upper limit of normal (eg, 10 mg/dl or: 2.5 mmol/l).
 - e. Neutrophil greater than the upper limit of normal (eg, greater than 7.0×10^9 dl).
 - f. Platelets greater than the upper limit of normal (eg, greater than 400 000).
 - g. Lactate dehydrogenase greater than 1.5 times the upper limit of normal.
 - h. Fuhrmann grade of tumour.
 - i. Tumour subtype eg, clear cell vs. non-clear cell.
6. Safety and tolerability data reporting for first line sunitinib.

Second line:

1. What is the OS of all patients in second line with axitinib, and stratified by MSKCC risk (favourable, intermediate, poor)?
2. What is the duration of therapy with axitinib in second line (using TTD) for all patients and stratified by MSKCC risk (favourable, intermediate, poor).
3. ORR.
4. Duration of ORR (CR or PR).
5. Examine factors that predict duration of therapy on axitinib (TTD), eg, risk stratification, or individual/grouped parameters that comprise the prognostic classification systems.
 - a. Less than one year from time of diagnosis.
 - b. Karnovsky performance status less than 80%.
 - c. Haemoglobin less than the lower limit of normal (eg, less than 12 g/dl).

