PFS will be measured from the index date of each treatment line to the date of progression, or date of death due to any cause, or date of initiation of new regimen. Patients who are still alive and have not progressed at the last office visit date without clinical or radiographic evidence of progression will be censored (final study cutoff will be June 2017). PFS will be estimated in months using the Kaplan-Meier method with 95% CIs, and summary tables of the number of events and censored patients at each month interval included. Kaplan-Meier plots for PFS will be presented for the overall population and stratified by MSKCC/IMDC risk category (favourable, intermediate, poor). A log rank test will be performed to compare the stratification groups.

Secondary Endpoints

All secondary endpoints will be analysed as follows:

Overall survival (OS)

OS will be defined as the time between the index date (dependent on treatment line) and the date of death from any cause. Patients who are still alive at the study end date or the last visit date available will be censored (using whichever occurred first). If a death date is known beyond the study end date, then the study end date (June 2017) will be used as the censoring

date. Median OS will be estimated in months using the Kaplan-Meier method with 95% confidence intervals (CIs), and summary tables of the number of events and censored patients at each month interval included. Kaplan-Meier plots will be presented for Overall Survival for the overall population, and stratified by MSKCC/IMDC risk (favourable, intermediate, poor). A log rank test will be performed to compare the stratification groups.

Best overall response (BOR)

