In prospective clinical trials, BOR is generally assessed according to the Response Evaluation Criteria In Solid Tumours (RECIST) 1.1.¹³ However, the parameters underlying these criteria are less reliably available in retrospective, observational studies. While an attempt will be made to mimic the RECIST guideline, it should be noted that assessments based on information garnered during routine clinical practice could be more subjective than assessments in a controlled clinical trial and decision making about continued therapy could include symptomatic criteria. Additionally, timing of repeat imaging may vary. All evaluation in this observational study will be as best determined by clinicians, either as noted in the patient chart by the radiologist-written scan report or the treating physician's progress notes or as interpreted by the clinician reviewer. The BOR for a line of treatment is the best response across all timepoints during that line of therapy assessed using the following categories: Complete response (CR), Partial Response (PR), Stable Disease (SD), Progressive Disease (PD), Not Evaluable (NE).

Objective response rate (ORR)

BOR will be summarized as ORR, which is defined as the number of patients having reached a BOR of CR or PR divided by the number of patients (the primary analysis population), including the NE patients.

ORR = Number of patients achieving a response (BOR = PR or CR)/Number of patients (BOR=CR+PR+SD+PD+NE).

Patients who do not have a BOR assessment for a particular line of therapy will be excluded from the summary for that line of therapy. The number of patients with a missing BOR assessment will be summarized.

Duration of response (DOR)

DOR will be calculated for each patient with a BOR of CR or PR as the duration of time from first documented CR/PR, to the earliest date of first progression or recurrent disease, or date of death, or date of initiation of new regimen. Patients who are still alive and did not progress will be censored at the last physician office visit date without clinical or radiographic evidence of progression. DOR will be estimated in months using Kaplan-Meier method with 95% CIs, and summary tables of the number of events and censored patients at each month interval included.

Time to treatment discontinuation (TTD)

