TTD will be calculated as the duration between the start of a treatment line to the end of the treatment line for patients with discontinuation of treatment for any reason, or censoring if a stop date is not documented (at end of study), if the patient dies, is lost-to follow up, or is still on-therapy. Patients without a discontinuation event will be censored on the study end date or at last office visit date without clinical or radiographic evidence of progression, whichever occurred first. Time to TTD will be analysed using the Kaplan-Meier method with 95% CIs, and summary tables of the number of events and censored patients at each month interval included.

Durable response rate (DRR)

DRR will be determined as the proportion of patients with objective response (CR or PR) with a duration of at least 6 months. Duration of response will be calculated as previously defined for DOR.

Time-to-Event Analysis

The Kaplan-Meier method will be used to estimate median OS, PFS and TTD. P values comparing survival curves by stratification groups, will be calculated using log-rank tests. Univariate and multivariable Cox proportional hazards regressions will be used to evaluate explanatory factors and to calculate hazard ratios (HRs) with two-sided 95% CIs for OS, PFS and TTD. Demographic and clinical factors will be included in multivariable Cox regression models based on their clinical relevance and/or the univariate significance level (assessed at the level of $p < 0.05$).

In order to account for the impact of baseline patient and disease characteristics outlined in this protocol and the disease characteristics below, unadjusted Cox models and multivariable Cox models adjusting for selected patient demographics and clinical characteristics identified by Pfizer as clinically relevant will be included in the adjusted models. Time-to-event analyses will be assessed in the overall population and by stratifications of interest (MSKCC/IMDC category). The disease characteristics of interest are:

- a. Less than one year from time of diagnosis;
- b. Karnovsky performance status less than 80%;
- c. Haemoglobin less than the lower limit of normal (eg, less than 12 g/dl);
- d. Serum calcium greater than the upper limit of normal (eg, 10 mg/dl or: 2.5 mmol/l);
- e. Neutrophil greater than the upper limit of normal (eg, greater than 7.0×10^9 dl);
- f. Platelets greater than the upper limit of normal (eg, greater than 400 000);

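### The TTD censoring date carries a progression condition that does not belong to the TTD event, so patients still on drug past progression at cut-off are censored too early

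*Combined protocol and SAP*

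**What the plan says.** The TTD paragraph of Section 9.7 takes as its event "discontinuation of treatment for any reason". It lists who has no event: "censoring if a stop date is not documented (at end of study), if the patient dies, is lost-to follow up, or is still on-therapy". The next sentence sets the date for everyone without an event: "censored on the study end date or at last office visit date without clinical or radiographic evidence of progression, whichever occurred first".

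The neighbouring endpoints in Section 9.7 read differently:

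- **PFS:** "Patients who are still alive and have not progressed at the last office visit date without clinical or radiographic evidence of progression will be censored". The phrase applies only to patients who have not progressed.
- **DOR:** patients alive and without progression are censored at the "last physician office visit date without clinical or radiographic evidence of progression". The same limit applies.
- **OS:** "Patients who are still alive at the study end date or the last visit date available will be censored". There is no progression condition.

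On continued treatment, the BOR paragraph remarks that "decision making about continued therapy could include symptomatic criteria". It gives no frequency.

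**The concern.** In PFS and DOR progression is an event, so a last progression-free visit is a sensible censoring date for patients who have not progressed. In TTD progression is not an event, and the sentence is not confined to patients without progression. It therefore reaches back behind time during which a patient is known to have been on drug. Whether post-progression treatment time counts then depends on how it ends: in full if a stop is recorded, not at all if the patient is still on drug at cut-off.

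TTD is a secondary endpoint in both lines, overall and by MSKCC risk group. It is also the outcome for the predictor objectives in Section 8 and for Cox models in Section 9.7. Duration of therapy on axitinib enters exploratory objective 6 as well.

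**Working it through.** The plan gives no TTD estimate, power or precision figure to reproduce (Section 9.5 says no power calculation was done). The check is therefore of the rule itself, followed by its size under assumed inputs.

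**1. One patient (illustrative).** Last clear visit at month 4, progression at month 6, still on drug at cut-off at month 12. The rule censors at month 4 and drops 12 − 4 = 8 months of known treatment. With a stop recorded at month 12, the same patient contributes 12 months and an event.

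**2. Direction.** Each Kaplan-Meier factor is 1 − d/n, with d stops among n at risk. Moving a censoring date earlier leaves every d unchanged and can only reduce n. So S(t) under the rule is at or below S(t) with censoring at the last on-drug date, at every t. This holds for patients known to be on drug after the date the rule assigns them.

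**3. Ten patients (illustrative, deliberately severe).** Six recorded stops, at months 4, 6, 8, 10, 14 and 18; the other four patients are censored.

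- Last on-drug date: n at risk 10, 9, 8, 7, 5, 3. S = 0.90, 0.80, 0.70, 0.60, 0.60 × 4/5 = 0.48, 0.48 × 2/3 = 0.32. Median 14 months.
- Plan's rule: n at risk 10, 8, 5, 3, 2, 1. S = 0.90, 0.90 × 7/8 = 0.788, × 4/5 = 0.63, × 2/3 = 0.42, × 1/2 = 0.21, 0. Median 10 months.

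**4. Size, large-sample simulation.** All inputs are assumed: median time to progression 6 months, 30–50% treated past progression for a further median of 3–6 months, other stops with median 30 months, visits every 2 months, accrual over 24–48 months, no on-drug deaths. Between 2% and 12% of patients are back-dated, and the median falls by about 1–9% against censoring at cut-off. Examples: 7.93 to 7.26 months with 24 months' accrual (0.67/7.93 = 8.4%), and 7.92 to 7.57 with 48 months' (0.35/7.92 = 4.4%). A sunitinib-like cohort accrued over 15 years loses under 1%.

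**5. Size at the expected numbers (163 axitinib, 678 sunitinib, Section 9.5).** Assumed: median time to progression 6 and 9 months respectively, toxicity stops at 0.02 per month, visits every 1.5 months, no missing stop dates, no on-drug deaths. The comparator censors at the last visit on drug. Values are medians over repeated simulations.

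| n | Past progression; extra median; follow-up window (months) | Plan's rule | Last on-drug visit | Fall | True |
|---|---|---|---|---|---|
| 163 | 10%; 3; 24 | 5.33 | 5.35 | 0.4% | 5.47 |
| 163 | 30%; 6; 24 | 6.21 | 6.49 | 4.2% | 6.75 |
| 163 | 50%; 12; 24 | 7.62 | 9.05 | 15.8% | 9.44 |
| 678 | 10%; 3; 120 | 7.51 | 7.52 | <0.1% | 7.51 |
| 678 | 50%; 12; 120 | 11.50 | 11.84 | 2.9% | 11.88 |
| 678 | 50%; 12; 60 | 10.98 | 11.74 | 6.5% | 11.93 |

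The tail moves more. In the third row S(24 months) is 0.04 under the rule, 0.18 with the last on-drug visit, and 0.20 in truth.

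**6. Net effect with the paragraph's other censoring rules.** n = 163, 30% past progression, 6 extra months, 36-month window; the true value counts an on-drug death as a discontinuation.

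| Scenario | Plan's rule | Last on-drug visit | True |
|---|---|---|---|
| Neither | 6.41 | 6.58 | 6.73 |
| 10% stop dates missing | 7.07 | 7.41 | 6.80 |
| 20% stop dates missing | 7.71 | 8.15 | 6.81 |
| 10% die on drug | 7.01 | 7.29 | 6.83 |
| 20% die on drug | 7.70 | 8.16 | 6.74 |

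The net error changes sign once missing stops or on-drug deaths reach 10%.

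**The case against.** The tempting stronger reading is that the plan understates TTD. The documents do not support it. The rule also dates patients who died on drug, were lost, or stopped without a recorded date. Losing those events pushes TTD up, and for an undocumented stop the last progression-free visit can even fall after the true stop. In the last table, correcting the back-dating alone moves the median further from the truth whenever such cases are present. This objection stands. It limits the claim to one component, but an offsetting error of unknown size is no reason to keep a wrong date.

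The bracketed remark in "censoring if a stop date is not documented (at end of study), if the patient dies, is lost-to follow up, or is still on-therapy" can be read as censoring undocumented stops at study end, in which case no back-dating arises for them. That is a fair reading, but it contradicts the sentence that follows, and it would credit patients lost to follow-up with treatment up to June 2017. The paragraph needs rewriting either way.

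The shift may also be small beside sampling error. For 163 patients and a median near 7.9 months, an exponential approximation without censoring gives a standard error of (7.9/0.693)/√163 ≈ 0.9 months, above the 0.35–0.67 months in step 4. That bears on priority, not on correctness.

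Three further inferences go too far. The BOR remark makes treatment past progression possible, not expected. Distorted risk-group comparisons or hazard ratios are conceivable, but no stratified check was made and their direction is unknown. That the phrase was carried over from PFS is a guess from similar wording; DOR has nearly the same phrase.

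**Conclusion.** The rule is wrong as written for patients known to be on drug past progression at cut-off: their censoring date is too early and depends on outcome. The downward direction of this component follows from the arithmetic, with recorded stops held fixed. The net direction of error in TTD is not established.

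The size rests wholly on assumed inputs, because the documents give neither the share treated past progression, nor the share on drug at June 2017, nor the visit spacing. It ranges from negligible (sunitinib, long accrual) through about 1–9% of the median (axitinib-like, short follow-up) to about 16% in the most extreme case tried. This is a correction worth making to a secondary endpoint of a descriptive study. It does not touch the primary PFS analysis.

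**What to change.** In the TTD paragraph of Section 9.7, remove the progression qualifier from the censoring sentence and state, for example: *Patients with no discontinuation event are censored at the last visit at which they are documented as on the drug, or at the June 2017 cut-off if earlier, regardless of progression status.* Reconcile the bracketed end-of-study remark in the preceding sentence so that one censoring date applies. Report separately, by line, the numbers still on drug, dead on drug, and with a missing stop date, so that readers can judge the upward components. Keep the progression wording for PFS and DOR only.

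The text change is small, and the current rule already needs visit dates. The real cost is in derivation. Section 9.3 lists start date, discontinuation date and reason, but no last date known to be on drug. That date must be built from visit and treatment records, with a chart query where no stop is recorded; Section 9.6 already provides for queries on missing data. Censoring at a visit still leaves a slight shortfall (9.05 against a true 9.44 months in the strongest case above).

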9.3. Variables

Variable	Operational definition
Demographic details	Anonymised, linked details
Diagnosis Date	Date of diagnosis
Diagnosis	Renal cell carcinoma: clear cell, non-clear cell
Prior surgery eg, nephrectomy	Yes/No; add details as necessary
Line of therapy	1 st line, 2 nd line, 3 rd line
Start date	Start date of therapy
Drug treatment	Drug name
MSKCC Risk Grade	Numeric value, subcategorise if possible: favourable/intermediate/poor risk. Include individual parameters that comprise this grading system where possible
IMDC/Heng Risk Grade	Numeric value, subcategorise if possible: favourable/intermediate/poor risk. Include individual parameters that comprise this grading system where possible
ECOG performance status at outset	Numeric value with related functional level attributed to this
TNM Stage	3 part cancer staging system; provide details where possible
Histology; Fuhrmann grade	Histopathological diagnosis and grading system
Metastasis diagnosis, if applicable	Site and extent of metastatic disease
Response to treatment	PFS, OS, TTD, Best overall response (BOR)
Date of discontinuation	Date of discontinuation of drug treatment
Therapy discontinuation	Reason for discontinuation

Data cut offs	Overall survival, loss to follow-up, withdrawal from study Data cut-off date for OS and PFS is June 2017
Adverse event reporting	It is expected that this data will have been reported through normal mechanisms, and will not have been recorded in the clinical database

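### The durable response rate has no rule for responders censored before 6 months and no clear denominator; read literally, it is biased low

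*Combined protocol and SAP*

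**What the plan says.** DRR has its own heading among the secondary endpoints in section 9.7: "DRR will be determined as the proportion of patients with objective response (CR or PR) with a duration of at least 6 months". The next sentence ties it to the preceding endpoint: "Duration of response will be calculated as previously defined for DOR".

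Under DOR, the clock runs from first documented response "to the earliest date of first progression or recurrent disease, or date of death, or date of initiation of new regimen". The censoring rule follows: "Patients who are still alive and did not progress will be censored at the last physician office visit date", provided that visit showed no sign of progression. DOR gets a Kaplan-Meier analysis with 95% CIs and monthly tables of events and censored patients.

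DRR gets no estimator beyond the proportion, no interval and no censoring rule. The general time-to-event paragraph in section 9.7 does not add one: "The Kaplan-Meier method will be used to estimate median OS, PFS and TTD".

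On follow-up, sections 9.1 and 9.2.1 take data from database inception (2002) to the end of June 2017, and section 9.3 states "Data cut-off date for OS and PFS is June 2017". The eligibility criteria in sections 9.2.1 and 9.2.2 set no minimum follow-up. Section 9.2 allows follow-up to end by withdrawal of consent or loss of contact.

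**The concern.** A threshold of at least 6 months can be applied to an event time without difficulty. It cannot be applied to a censored time without a further rule. A response that is still ongoing at month 4, when the patient's record ends, has a calculated duration of 4 months. Taken at face value it does not reach 6 months, so it leaves the numerator, although nobody knows whether it would have lasted.

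Some early censoring is to be expected, because treatment could start right up to the date on which the data stop. Censoring at the last visit, rather than at the cut-off, shortens follow-up further.

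The literal DRR therefore mixes how long responses last with how long responders were observed. The denominator is a second gap. The sentence can mean the share of responders whose response lasts 6 months, or the share of all patients who have such a response. Two programmers could follow the text and report different figures.

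**Working it through.** The plan states no DRR, response rate, median DOR or censoring rate, so there is no figure to reproduce. What follows is illustrative.

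**Inputs**
- Threshold of 6 months, and DOR censored at last visit: section 9.7.
- Data window from 2002 to the end of June 2017: section 9.2.1. This is 174 to 186 months, depending on when in 2002 the database began.
- Assumed: exponential DOR with median 12 months (range 6 to 18); censoring independent of DOR; first response at month 3; uniform accrual.
- c = share of responders whose available follow-up after first response is under 6 months. It is not in the documents.

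**True 6-month value.** S(6) = 2^(−6/12) = 0.707.

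**Literal rule.** A responder counts only if the response lasts 6 months and follow-up also reaches 6 months, so the expected DRR is S(6) × (1 − c).

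**Values of c under uniform accrual.** With response at month 3, c = 6 / (window − 3).
- Full window: 6/183 = 3.3% to 6/171 = 3.5%.
- Shorter windows, assumed because the documents give no start date for either drug: 6/57 = 10.5% for 60 months and 6/33 = 18.2% for 36 months.

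These count only the June 2017 cut-off. Last-visit censoring and loss of contact would add to c by an unknown amount.

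| c | Literal DRR (true 0.707) | Shortfall, points |
|---|---|---|
| 0 | 0.707 | 0 |
| 3.5% | 0.707 × 0.965 = 0.682 | 2.5 |
| 10% | 0.707 × 0.90 = 0.636 | 7.1 |
| 20% | 0.707 × 0.80 = 0.566 | 14.1 |

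For median DOR between 6 and 18 months, the shortfall is S(6) × c: 5.0 to 7.9 points at c = 10%, and 10.0 to 15.9 points at c = 20%.

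**Other rules the text would allow.** Take exponential censoring at rate μ = −ln(1 − c)/6 and event rate λ = ln 2/12. The share with an observed event before 6 months is E = λ/(λ + μ) × (1 − e^(−6(λ + μ))). At c = 10%, E = 0.279.
- Censored responders excluded: 0.636 / (0.636 + 0.279) = 0.695, slightly low.
- Censored responders counted as durable: 1 − 0.279 = 0.721, slightly high.
- Share actually seen as censored before 6 months: 1 − 0.636 − 0.279 = 8.5%. This is a little below c, because some responders have their event first.

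**Kaplan-Meier check.** In 4,000 simulated sets of 60 responders (an assumed number) with median 12 months, the 6-month Kaplan-Meier estimate averaged 70.7% at c = 10% and at c = 20%. The literal proportion averaged 63.6% and 56.6%.

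**Denominator.** If all patients are meant, both figures are scaled by the objective response rate (ORR) and the relative loss is unchanged. With an assumed ORR of 30% and c = 10%, 21.2% becomes 19.1%.

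**The case against.** The plan never says that a responder censored early is a failure. A reader might infer that it prescribes a downward-biased estimator and that the bias is always downward. The documents do not support that: they are silent, and the direction depends on the missing rule. Downward bias follows from the literal reading and, more weakly, from exclusion. Counting such responders as durable would bias DRR upward. This objection stands, and it makes the defect an unspecified rule first and a bias second.

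The size also has no anchor in the documents. The only stated window gives c of about 3.3% to 3.5% under uniform accrual. Rows with c of 10% or 20% need shorter drug-specific windows or losses that the documents do not report. The cut-off sentence in section 9.3 names OS and PFS, not DOR, although sections 9.1 and 9.2.1 close the data window for everything.

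A reader might also infer that a sunitinib-versus-axitinib comparison is distorted. Unequal accrual windows could make the literal DRRs differ at equal durability, but no objective in section 8 compares the two drugs, and section 9.5 calls the analysis descriptive.

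Finally, DRR appears in no objective, and the planned DOR curve and monthly tables already contain the 6-month estimate and the early-censoring counts. That limits the harm. It does not correct a DRR reported beside them on a different footing.

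**Conclusion.** The point holds as a gap in the definition: no rule for responders censored before 6 months, no stated denominator and no interval. On the literal reading, DRR is low by the factor (1 − c). With an assumed median DOR of 12 months, that is about 2.5 points if c is 3.5%, 7 points at 10% and 14 points at 20%, and nothing if every responder has at least 6 months' follow-up. These figures rest on assumed durations, independent censoring and assumed values of c, so they show sensitivity and do not predict the study's result. Severity is modest, because DRR is a secondary endpoint in section 9.7 that the objectives do not name, and the better estimate lies in output already planned. It is still worth correcting before the analysis is run.

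**What to change.** Replace the DRR definition in section 9.7 with the following:

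- DRR among responders is the Kaplan-Meier estimate of DOR at 6 months with its 95% CI, for each treatment line, taken from the planned DOR analysis.
- The number of responders censored before 6 months is reported beside it.
- If an all-patient figure is also wanted, it is ORR multiplied by that estimate, with a delta-method or bootstrap CI. Its denominator is patients with a best overall response assessment, because section 9.7 leaves those without one out of the ORR summary. It should not be labelled as covering all treated patients.

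The cost is a few sentences and, for the all-patient figure, one extra interval calculation. No new data are needed. The estimate assumes that censoring is unrelated to the remaining duration of response, which the planned DOR curve assumes already.
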